9.1.1. Incidence of Adverse Events

A Treatment-Emergent AE (TEAE) will be defined as any AEs, regardless of relationship to study drug, that occur after the first dose of double-blind study drug and within 14 days after the last dose of double-blind study drug. An AE with a reported onset date after the subject has signed the informed consent document and before the date of randomization (or the date of first dose of study drug if a subject was treated but no randomized) will be considered a pre-study event. AEs with missing onset dates will be considered on-study events.

If the day of onset of an AE is missing, and if the month and year of an onset date are on or after Day 1, general imputation rules from [section 4.5](#) will be applied.

If, despite implementing the above conventions, the onset date of the AE cannot be placed before, on, or after Day 1, then the event will be considered on-study.

All AEs will be coded using the MedDRA Version 17.0 or higher coding system. In this dictionary, each diagnosis is mapped to a lower level term and then to a preferred MedDRA term, which is then mapped to a system organ class.

TEAEs will be summarized by treatment group and overall for the SS. Summaries of TEAEs will be displayed by descending overall frequency for system organ class and preferred term. Treatment-Emergent AEs and SAEs will include events per 100 subject-years of study drug exposure. In addition, TEAEs leading to Study Drug Discontinuation, Serious TEAEs and TEAEs resulting in Deaths will be presented.

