8.2.3.3 SAE Reporting to Sponsor

All SAEs must be reported, whether or not considered attributable to the study drug, on a separate SAE report form. As much information as possible should be supplied at the time of the initial report with at least the following information:

- Subject, treatment, and study identifiers;
- Investigator's name and address;
- Description of the event, action taken, and outcome;
- Date of onset and current status;
- Any suspect (study) drug, with its start date, dose, and form of administration;
- Reason the AE is regarded as serious;
- Current assessment or opinion of causality;
- Any other available diagnostic information that will contribute to the understanding of the event; and
- If applicable, whether the randomization code has been broken because of the SAE.

The Investigator must inform the Sponsor or Sponsor's designee within 24 hours of when the Investigator is aware of the occurrence of the SAE, whether or not the SAE is related to the study drug. A written report should be submitted, consisting of the SAE report form accompanied by the demographics, medical history, AE, and the concomitant medications pages from the study documents. All pertinent information must be followed by a full follow-up report to the Sponsor within 3 calendar days. As complete a report as possible, (e.g., results of any additional tests) should be forwarded within 8 additional calendar days to the Sponsor. Any significant new information on the SAE and final outcome must be supplied promptly to the Sponsor.

SAEs will be collected throughout the study beginning at Screening and continuing for the duration of the study. Ongoing SAEs will be followed to resolution, whenever possible.

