3.4. Study Drug Interruption/Discontinuation

Treatment may be interrupted or discontinued at the discretion of the Investigator and Sponsor, based on AEs, other clinical laboratory data, vital signs measurements, and/or electrocardiogram (ECG) findings.

Subjects discontinuing study drug will continue participation in the study and will complete all remaining study visits. Discontinuation of assigned study drug (RVX000222 or placebo) or high intensity statin therapy should not result in study discontinuation.

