7.1. Study Treatments

7.1.1. Study Drug Exposure

RVX000222 or matching placebo will be taken orally with meals in the morning and in the evening, 10-12 hours apart.

Table 2: Study Drug Administration Schedule

Treatment Group	Daily dose (mg)	Dose administration b.i.d. (mg)	AM Dose (mg)	PM Dose (mg)	No. of capsules/day
A: RVX000222	200	100	100	100	2
B: Placebo	0	0	0	0	2

As described in [section 3.8](#), if subjects have elevated ALT values they may be administered study drug or matching placebo at a reduced dose of 50 mg b.i.d. This dose change information is to be collected in the eCRF as action taken with study drug when reporting elevated ALT values as an adverse event and subject to confirmation by the medical monitor. Subjects with at least one study treatment dose reduction and those with none will be represented by treatment group on FAS. Information on number of subjects by number of dose reductions will also be summarized by treatment group.

Study drug exposure will begin on the day of the first dose of study drug and end on the day of the last dose of study drug. Duration of study drug exposure in months will be defined as (date of last dose - date of first dose + 1)/30.4.

Study participation will begin on the day of randomization and end on the day of last contact. Duration of study participation in months will be defined as (date of last contact – date of randomization +1)/30.4.

Duration of exposure to study drug and duration of study participation will be summarized for the FAS using descriptive statistics. Duration of study drug exposure and duration of study participation will also be categorically summarized by number and percentage of subjects who had at least 12-weeks, greater than 12 weeks up to 24 weeks, greater than 24 weeks up to 52 weeks, and greater than 52 weeks of study drug exposure and study participation. Duration of drug exposure on subjects with at least one dose reduction will be summarized by the aforementioned categories.

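### SAP 9.1.1 counts treatment-emergent events to 14 days after the last dose but divides by first-to-last-dose time, and does not say which SAEs enter the rate

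*SAP*

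**What the plan says.** SAP 9.1.1 (Incidence of Adverse Events) sets the rate: "Treatment-Emergent AEs and SAEs will include events per 100 subject-years of study drug exposure".

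The denominator is defined in SAP 7.1.1 (Study Drug Exposure): "Study drug exposure will begin on the day of the first dose of study drug and end on the day of the last dose". Interruptions are not subtracted. The same section defines a longer time base that the rate does not use: "Study participation will begin on the day of randomization and end on the day of last contact".

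The TEAE numerator runs from the first dose to any onset "within 14 days after the last dose of double-blind study drug" (SAP 9.1.1).

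For SAEs, Protocol 8.2.3.3 says that "SAEs will be collected throughout the study beginning at Screening and continuing for the duration of the study", and SAP 9.1.4 defines an SAE without a time window. Follow-up goes on after drug is stopped: "Subjects discontinuing study drug will continue participation in the study and will complete all remaining study visits" (SAP 3.4). SAP 3.7 adds a Follow-Up Visit 4 weeks after the Last Visit on Treatment.

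**The concern.** A rate per subject-year is interpretable only if events and person-time cover the same period. Here the TEAE window extends 14 days past the point where the person-time stops, so every TEAE rate is biased upward.

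The SAE part could be larger, and it turns on what SAEs means in the quoted sentence:

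- **Treatment-emergent SAEs.** The adjective may govern both nouns, and SAP 9.1 and Protocol 9.7 describe the serious subset as treatment-emergent.
- **All on-study SAEs.** The next sentence of SAP 9.1.1 adds serious TEAEs as a further display, which suggests that the SAEs just named are something else.

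Under the second reading, events after early drug stop and during the 4-week follow-up are counted, while that time is left out of the denominator. Potential MACE are reported as SAEs (Protocol 8.2.3.5), so in this post-ACS population such events would not be rare. The denominator wording also varies: SAP 9.1.2 and 9.1.3 call it study exposure, without the word drug. Two programmers could defend different tables.

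**Working it through.** **Inputs (SAP 4.2 unless noted).** Uniform accrual over 1.7 years; total duration 2.75 years including follow-up; drop-out 5% by year one; event rates 10.5% and 7.47% at 18 months; 250 events; hazard ratio 0.7; two-sided 5%. The 14-day window is from SAP 9.1.1 and the 4-week (28-day) follow-up from SAP 3.7. The documents state no AE rate, SAE rate or drug-stop rate.

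**Check of the design figures.** The plan has no AE figure to reproduce, so I checked the follow-up inputs against its power and event count.

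- Power = Φ(√(250/4) × |ln 0.7| − 1.96) = Φ(2.82 − 1.96) = 0.805, against a stated value of approximately 80%.
- Exponential hazards with 1,200 subjects per arm give 149.0 + 106.5 = 255.5 expected events, against 250 needed.

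**Mean follow-up.** Drop-out hazard λ = −ln 0.95 = 0.0513 per year. Averaging (1 − e^(−λu))/λ over u from 1.05 to 2.75 years gives 1.805 years, or 659 days. The share not dropping out is 1 − 0.0513 × 1.805 = 0.907.

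**Mean exposure with no early stop.** If treatment ends 28 days before study end for those who remain, mean exposure is 659.2 − 28 × 0.907 = 633.8 days.

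**TEAEs and serious TEAEs.** Overstatement = (extra days counted)/(exposure days).

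- No early stop: 14 × 0.907 / 633.8 = 2.0%.
- Simulation with 10-20% stopping early: 2.1-2.3%.
- Ratio between arms with 3-5% more stopping at Week 8 in one arm: about 1.001.
- By individual exposure, 14/E: 8.3% at 24 weeks, 3.8% at 1 year, 2.6% at 1.5 years.

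**All on-study SAEs, if that is what is meant.** Overstatement = (mean follow-up)/(mean exposure) − 1. If a fraction p stops drug at a uniformly distributed time, mean exposure is 633.8 × (1 − p/2).

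| Stop early (assumed) | Mean exposure, days | Overstatement |
|---|---|---|
| 0% | 633.8 | 4.0% |
| 10% | 602.1 | 9.5% |
| 20% | 570.4 | 15.6% |

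**Between arms, same reading.** Assume equal true rates and an excess x of RVX000222 subjects stopping at day 56. The spurious ratio is 633.8 / [633.8 × (1 − x) + 56x].

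- x = 3%: 633.8/616.5 = 1.028.
- x = 5%: 633.8/604.9 = 1.048.

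A second stopping model, with constant stop hazards of 0.05-0.12 per year (about 9-19% stopping), gives overstatement of 9-17%. Its ratios are 1.03 (13% against 9% stopping) to 1.07 (19% against 9%).

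**Limits.** Death is not modelled separately. A subject who dies on drug has no off-drug tail, so these figures are slight upper bounds.

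**The case against.** The best defence is that the rate covers treatment-emergent events only. The sentence sits in a paragraph on TEAE summaries, and SAP 9.1 and Protocol 9.7 both list the serious subset as treatment-emergent. Protocol 8.2.3.3 shows that SAEs are collected throughout, not that all of them enter this rate. Read literally, all SAEs would even include screening events, which SAP 9.1.1 classes as pre-study. On this reading only the 2% remains, and it is nearly the same in both arms. This defence is fair, but the SAP does not settle the question, because the following sentence points the other way.

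A reader might go further and infer that the SAE rates will be overstated by 4-16% and will show a false excess on RVX000222. The documents do not support that as a flat statement, for three reasons.

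- It needs the all-SAE reading.
- It needs stop rates, overall and by arm, that are nowhere given.
- The liver mechanism is plausible but narrower than it looks. The 7-8% in Protocol 1.0 is ALT above 3×ULN, while SAP 3.8 discontinues drug for confirmed ALT above 5×ULN and allows restart where another cause is found. Temporary interruptions do not shorten first-to-last-dose exposure.

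The consequence is also bounded. Safety is descriptive (SAP 9), no SAE rate ratio is planned, and MACE is compared by adjudicated time-to-event analysis. Exposure and participation durations are both tabulated, so unequal stopping would be visible. All of this stands. It limits the weight of the point but does not remove the mismatch.

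**Conclusion.** The mismatch is certain for TEAEs and serious TEAEs. It amounts to about 2% at the design's mean follow-up, is nearly equal between arms, and would not by itself change a safety conclusion.

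The SAE part is an ambiguity with a conditional cost. Only if all on-study SAEs are counted is the rate overstated by about 4% with no early stopping and about 9-16% with an assumed 10-20% stopping early. Only on that reading, and with an assumed 3-5% excess of early stopping on RVX000222, does a spurious ratio of about 1.03-1.05 appear. A differential bias is therefore possible but not established.

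The point is worth correcting before unblinding. With no inferential safety analysis, readers will compare the printed rates directly, and the text permits two tables that differ by several percent.

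**What to change.** In SAP 9.1.1, state which SAEs enter the rate and define person-time to match:

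- **TEAEs and serious TEAEs:** first dose to the earliest of last dose + 14 days, death and last contact.
- **All on-study SAEs, if wanted:** count only those with onset after the first dose, and use first dose to death or last contact.

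Use the same denominator term in SAP 9.1.2 and 9.1.3.

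The cost is a small text change and one extra derived person-time variable (one for each numerator if both rates are printed). The dates of first dose, last dose, last contact and death are already used in SAP 7.1.1 and 9.1.7. Printed rates become slightly lower. No hypothesis test, data collection or treatment rule changes.

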9.1.2. Relationship of Adverse Events to Study Drug

Numbers and percentages of subjects with TEAEs by causality and study drug-related TEAEs will be summarized by system organ class and preferred term; TEAE with missing relationship to study drug will be considered as study drug-related and included. However, the TEAE will be presented with a missing relationship. Drug-related TEAEs will be defined as any TEAE that the investigator considers related to study drug. If a subject reported multiple occurrences of the same AE, only the

related occurrence will be presented. Therefore, these summaries will not include events per 100 subject-years of study exposure.

9.1.3. Intensity of Adverse Event

Numbers and percentages of subjects with TEAEs by intensity, system organ class and preferred term will be summarized; AEs with missing intensity will be imputed. If a subject reported multiple occurrences of the same AE, only the most severe occurrence will be presented. Therefore, these summaries will not include events per 100 subject-years of study exposure.

9.1.4. Serious Adverse Events

An SAE or reaction is any untoward medical occurrence that at any dose:

- Results in death;
- Is life threatening (life threatening refers to an event in which the subject was at immediate risk of death at the time of the event; it does not refer to an event that hypothetically might have caused death if it were more severe);
- Requires inpatient hospitalization or prolongation of existing hospitalization;
- Results in persistent or significant disability or incapacity;
- Is a congenital anomaly or birth defect; or
- Is medically significant, and though not included in the above list, is an important medical event that may jeopardize the subject or require medical intervention to prevent one of the outcomes listed above. Discontinuation of study drug or conduct of additional diagnostic evaluations, will not, by themselves, satisfy the criterion for a medically significant event.

9.1.5. Hospitalization

Adverse events reported from clinical trials associated with hospitalization or prolongations of hospitalization are considered serious and will be included in SAEs.

Hospitalization does not include the following:

- Rehabilitation facilities
- Hospice facilities
- Respite care
- Skilled nursing facilities
- Nursing home
- Routine emergency room admission
- Same day surgeries (as outpatient/same day/ambulatory procedures)

9.1.6. Adverse Events Leading to Study Drug Discontinuation

AEs leading to study drug withdrawal will be recorded on the eCRF with a study drug action taken as “Drug Withdrawn”. Numbers and percentages of subjects with AEs leading to study drug withdrawal will be summarized by system organ class and preferred term. All AEs leading to study drug withdrawal will also be summarized.

9.1.7. Death

All deaths during this study will be reported. Data presented will include, where applicable, date of first dose, AE type, date of death, days relative to the date of randomization, date of last dose, study day, cause of death, and relationship of cause of death to study drug.

9.2. Clinical Laboratory Evaluations

Clinical laboratory samples (fasting lipid panel, hematology, chemistry, hepatitis serology, liver safety, lipoproteins, and inflammation panel) will be collected according to the study Schedule of Events shown in the protocol.

Evaluation of clinical laboratory samples collected for safety will include standard hematology, serum chemistry, and urinalysis. All summaries of clinical laboratory variables will be performed using the SS. No inferential statistics will be provided.

Change from baseline in continuous safety laboratory variables will be summarized by treatment group. Standard units will be reported for all lab tests.

In the event that 2 or more observations equidistant from the expected visit date are available, the later observation will be used. A subject who has multiple test results for a particular test at a particular visit and at least 1 of them is markedly abnormal; the subject will be classified as having a markedly abnormal result at that visit and values from all visits will be listed. All descriptive statistics will be based on data selected according to the window convention outlined in [Section 4.5](#).

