Overall, RVX000222 was generally well tolerated and AEs were mild with little discernible difference between placebo- and the RVX000222-treated subjects. The dose-limiting toxicity for RVX000222 is a generally non-symptomatic elevation in serum transaminases (alanine aminotransferase [ALT] and in some cases aspartate aminotransferase [AST]), without adversely affecting total bilirubin values in any subject. There was no increase in alkaline phosphatase (ALP) observed. There was an overall incidence of 7-8% of subjects with ALT >3x the upper limit of normal range (ULN). There was often confounding with use of drugs known to increase ALT (diclofenac and clavulanic acid) or prior history of hepatitis. Raised enzymes return promptly to within the normal transaminase range (approximately 15 days for ALT >5xULN), suggesting that any hepatocellular effect can be reversed by suspending treatment with investigational drug. For subjects with elevations >3xULN and <5xULN, treatment was continued and all returned to normal levels. Subjects with ALT elevations >5x and <8xULN were dose interrupted, re-challenged at a lower dose and the majority successfully completed the studies. Drug-induced ALT elevations >3xULN were observed between weeks 4-12 across all 4 completed Phase 2 trials, with one exception. One subject with elevated ALT and AST at Week 20 due to cholecystitis was noted in RVX222-CS-007. No cases of Hy's Law have been detected.

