9.7 Safety Analysis

Drug administration, disposition data, medical history and prior medications will be summarized by treatment group using descriptive statistics. Safety data such as clinical laboratory results, vital signs, findings from physical examinations, and MOCAs will be listed and summarized by treatment group where appropriate. For continuous variables, these summaries will include sample size, mean, median, standard deviation, minimum, and maximum. For categorical variables, these summaries will include frequencies and corresponding percentages. No inferential hypothesis testing will be performed on the safety variables.

The assessment of safety will be based on the frequency, intensity, and types of AEs and for change and shift from Baseline in the clinical laboratory variables, and vital sign measurements. Baseline values for clinical laboratory variables, and vital sign measurements are defined as the last non-missing values obtained prior to dosing. Clinical laboratory variables outside reference ranges will be flagged in clinical laboratory listings.

Adverse events will be summarized using the safety set. Adverse events will be coded using MedDRA (version 17.0 or higher), summarized by frequency, severity, relationship to study drug, and number of subjects per treatment and by the preferred term and system organ class. Data will be summarized using preferred term and primary system organ class. The coded events will be summarized by treatment group, in subsets of all treatment-emergent AEs, all treatment-related AEs, non-serious treatment emergent AEs and serious treatment emergent AEs. Adverse events of special interest (opportunistic infections and all serious/severe infections) will be analyzed as a subset of the overall AEs. Treatment-emergent AEs will be defined as any AEs, regardless of relationship to study drug, that occur after the first dose of double-blind investigational drug and within 14 days after the last dose of double-blind investigational drug. Treatment-related AEs will be defined as any AEs that are considered by the investigator to be either possibly, probably, or definitely related to study drug. In addition, if relationship information is missing, the AE will be considered treatment-related. Listings for the subsets of SAEs and treatment-related SAEs will be provided.

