4.5. Definition of Time Points, Study Dates, Visit Windows, and Duration

Study Day 1 is defined as the day of randomization when subjects will receive the first dose. Other study days are defined relative to Study Day 1, e.g. the day prior to Study Day 1 is Day -1 and the day after Study Day 1 is Day 2. Study days will not be computed for subjects who are not randomized.

All scheduled study visits will be defined relative to Study Day 1. For example, the appropriate day for the scheduled Week 2 visit should be: Day 1 + 14 = Day 15. A windowing convention which will be used to determine the analysis value for a given study visit will be applicable for all by-visit summaries and analyses. The study visit window can be found in the “Schedule of Events” in the study protocol and also presented in the following table below:

Table 1: Visit Windows for Efficacy and Safety Variables

Study Week	Scheduled Day	Study Day Range
0	Baseline (Day 1)	<=1
2	15	12 18
4	29	26 32
6	43	40 46
8	57	54 60
10	71	68 74
12	85	82 88
16	113	110 116
20	141	138 144
24	169	166 172
28	197	194 200
40*	281	274 288
52	365	358 372
64	449	442 456
76	533	526 540
88	617	610 624
100	701	694 708
112	785	778 792

*Visits to occur with +/- 7-day window past week 40 every 12 weeks

Study treatment will be terminated in all currently participating subjects when the 250th event occurs and all surviving patients have been followed for at least 24 weeks from randomization. At that time all subjects actively treated will conduct their Last Visit on Treatment. Follow up visit is to be scheduled 4 weeks after last visit on treatment. Last visit on treatment and follow up are subject to +/-7 day window.

The baseline value for a variable is defined as the last observation collected on or before Study Day 1/first dose date & time; it cannot be substituted for any post-baseline value. Unscheduled visits or Study visits that are outside the protocol defined windows will be mapped to the closest study visits. All safety data with incomplete dates will be forwarded to Data Management for query.

One or more results for a particular variable may be obtained in the same visit window due to unscheduled or repeated measurements. In such events, the result with the date closest to the expected visit date (scheduled day) will be used. In the event that 2 observations equidistant from the expected visit date are available, the later observation will be used.

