9.1. Adverse Events

Adverse events will be summarized using the safety set. Adverse events will be coded using MedDRA (version 17.0 or higher), summarized by frequency, severity, relationship to study drug, and number of subjects per treatment and by the preferred term and system organ class. Data will be summarized using preferred term and primary system organ class. The coded events will be summarized by treatment group, in subsets of all treatment-emergent AEs, all treatment-related AEs, and serious treatment emergent AEs.

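### The SAP specifies no by-arm count of subjects exceeding the protocol's ALT and bilirubin limits, and omits the laboratory shift analysis and AESI subset promised in Protocol 9.7

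*SAP*

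**What the plan says.** Protocol 1.0 describes the known toxicity: "The dose-limiting toxicity for RVX000222 is a generally non-symptomatic elevation in serum transaminases". It gives the rate, "There was an overall incidence of 7-8% of subjects with ALT >3x the upper limit of normal range (ULN", places the drug-induced cases in weeks 4-12 with one exception, and reports that this occurred "without adversely affecting total bilirubin values in any subject". Protocol 6.10.1 sets action limits at ALT >3xULN, ALT >5xULN and bilirubin >2xULN.

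The SAP repeats those limits in sections 3.8 and 9.2.5, but only as monitoring and dosing rules. Its stated laboratory analyses are:

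- SAP 9.2: "Change from baseline in continuous safety laboratory variables will be summarized by treatment group". All descriptive statistics follow the window convention of SAP 4.5.
- SAP 4.5: when several results fall in one window, "the result with the date closest to the expected visit date (scheduled day) will be used".
- SAP 8: liver function variables get N, mean, median, SD, quartiles, minimum and maximum by arm and visit.
- SAP 9.2: a subject with any markedly abnormal result at a visit is classed as such and the values are listed. No threshold is given and no table is named.
- SAP 9.2.5 (Liver Safety Panel): no summary is specified. The lipid, hematology, chemistry, lipoprotein, insulin and inflammation sections each specify one.

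Protocol 9.7 bases the safety assessment partly on laboratory data, "for change and shift from Baseline in the clinical laboratory variables", and adds: "Adverse events of special interest (opportunistic infections and all serious/severe infections) will be analyzed as a subset of the overall AEs". The SAP's adverse-event summaries are made "in subsets of all treatment-emergent AEs, all treatment-related AEs, and serious treatment emergent AEs". It has no AESI subset and no shift table.

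**The concern.** Drug-induced ALT elevation is an outlier signal: a small share of subjects rises well above the limit for a few weeks and then returns. By-visit statistics are a weak way to show it, because each subject contributes one value per window and different subjects are elevated in different windows. The direct summary is the number of subjects in each arm who ever crossed each limit, and the SAP text does not ask for it.

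The protocol does not fill the gap by default. Protocol 9.1 lets the SAP modify and supersede its statistical methods, so an analysis promised in Protocol 9.7 but absent from the SAP may not be produced. At stake is a clear between-arm statement on the dose-limiting toxicity, including how many subjects had ALT and bilirubin raised together, and on the infections chosen as AESIs.

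**Working it through.** **Inputs.** Earlier-trial ALT >3xULN rate, 7-8% (Protocol 1.0). About 2400 subjects randomized 1:1 (SAP 4.2, 4.3.1), so 2400 / 2 = 1200 per arm. Repeat tests every 3-4 days (Protocol 6.10.1). Scheduled days from SAP Table 1.

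**The plan's own figure.** The 7-8% cannot be reproduced: the protocol gives no numerator, denominator or placebo rate.

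**Expected count.** Rate x 1200: 0.07 x 1200 = 84 and 0.08 x 1200 = 96. The 95% half-width is 1.96 x sqrt(p(1 - p)/1200), which is 1.4 percentage points at 7% and 1.5 at 8%. An assumed placebo rate of 0.5-3% would be 6-36 subjects.

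**What by-visit statistics would show.** Assume 1-4% of active subjects are elevated in a given window, by 2.5-7xULN above baseline. Neither range is in the documents.

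- Mean shift = share x excursion: from 0.01 x 2.5 = 0.025xULN to 0.04 x 7 = 0.28xULN.
- If a share s sits above the rest, the median is the 0.5/(1 - s) quantile of the unaffected subjects. That is 0.505 at s = 1% and 0.521 at s = 4%.
- The 75th percentile likewise becomes the 0.758 to 0.781 quantile.
- The maximum shows that an extreme value exists, not how many subjects had one, and only if that value was the one selected.

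**What the window rule does to repeats.** Take a Week 6 result on its scheduled Day 43. A repeat 3-4 days later falls on Day 46 or 47. Day 46 is inside the Week 6 window (40-46). Day 47 is outside every window and maps to the closest visit, Week 6 (4 days away, against 10 for Week 8 on Day 57). In both cases the Day 43 result is closer to schedule and is kept. A higher repeat is therefore dropped from the descriptive statistics, even if it takes the subject past 5xULN.

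**What adverse-event capture recovers.**

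- ALT >5xULN or bilirubin >2xULN: Protocol 6.10.1 suspends drug, and Protocol 8.2.2 records laboratory values that cause interruption or discontinuation as adverse events. These reach the SAP 9.1.1 tables and, where applicable, the withdrawal (9.1.6) and dose-reduction (7.1.1) summaries.
- ALT >3 to 5xULN: the stated action is repeat testing and monitoring. Protocol 8.2.2 makes the value an adverse event only if it causes signs or symptoms, is judged clinically significant or needs therapy. The protocol describes these elevations as generally without symptoms.
- In either band, tables by preferred term carry no multiple of ULN.

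**Protocol 9.7 against the SAP.** The opening of SAP 9 repeats the protocol's sentence on laboratory change but without the word *shift*, leaving a stray *and*. No shift table appears elsewhere. AESI is absent from the SAP's adverse-event sections and from its abbreviation list.

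**The case against.** A reader might infer that the SAP summarizes liver safety only by mean change and would hide the toxicity. The documents do not support that. SAP 8 gives quartiles and the maximum. The *markedly abnormal* rule uses any result at a visit, not just the windowed one. Protocol 9.7 flags out-of-range values in listings. The more severe elevations reach adverse-event tables through suspension of drug. The data safety monitoring board reviews unblinded safety data quarterly (Protocol 10.8). Nor is bilirubin part of the known signal, since Protocol 1.0 reports no bilirubin effect.

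The windowing point also has limits. Liver panels are scheduled every two weeks through Week 12, which covers the risk period, so a first crossing would usually be found at a scheduled visit and kept. What can be lost is a later peak.

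The 84-96 may be too high. Earlier cases were often confounded by diclofenac, clavulanic acid or prior hepatitis. This trial restricts both drugs (Protocol 6.8) and excludes active hepatitis and ALT or AST >1.5xULN at screening (Protocol 5.3).

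The missing *shift* may be a typing slip rather than a decision, and serious infections would still appear in serious adverse-event tables. SAP 4.1 refers to table shells that are not in the documents, so a threshold table there cannot be ruled out.

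All of this narrows the point. None of it supplies a by-arm count of subjects above the limits, a threshold for *markedly abnormal*, a shift table or an AESI subset.

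**Conclusion.** The point holds in this limited form and should be corrected. The SAP text would present the dose-limiting toxicity incompletely. The main blind spot is asymptomatic ALT >3 to 5xULN with drug continued; the second is peaks found at unscheduled repeats. Two analyses promised in Protocol 9.7, laboratory shift and the AESI subset, are absent.

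The size rests on carrying the earlier 7-8% over to about 1200 active subjects, which gives about 84-96 above 3xULN and possibly fewer under this trial's restrictions. The documents do not say how many of these would fall in the >3 to 5xULN band. They give no placebo rate, so no between-arm difference can be stated. The small movement in visit means (about 0.03-0.28xULN) depends on assumed per-visit shares and excursions. The absence of the threshold table is established for the SAP text only, not for the unseen shells.

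**What to change.** In SAP 9.2.5, on the Safety Set and using all post-baseline results including unscheduled ones, add by arm:

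- n (%) of subjects with maximum ALT >3xULN and >5xULN;
- n (%) with maximum bilirubin >2xULN;
- n (%) with ALT >3xULN together with bilirubin >2xULN;
- baseline-to-worst shift tables, as Protocol 9.7 implies.

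Define *markedly abnormal* for the liver panel by these same limits. In SAP 9.1, restore the AESI subset (opportunistic infections and serious or severe infections) as Protocol 9.7 states. Time to first ALT >3xULN and AESI rates per 100 subject-years would be useful but are optional; Protocol 9.7 requires neither.

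The cost is a few more tables from data already collected. Visits, sample size and the efficacy analyses are unaffected.
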